Objective 4 (OUTCOMES): Improve and sustain **case management** of PPH and newborn resuscitation during observations of care, as measured by a) percent of women with undelivered placenta after 30 minutes who are

treated with oxytocin, and b) percent PPH cases that receive repeated dose of oxytocin or misoprostol, c) percent of newborns not breathing at birth who are breathing or being ventilated with bag & mask at one minute.

Objective 5 (IMPACT): Reduce over time: a) the percent of facility-based deliveries who experience PPH; b) the PPH-related case fatality rate, and c) the perinatal death rate (the fresh stillbirth rate and early newborn mortality rate at 24 hours or prior to discharge)¹.

Prior to presenting the hypotheses, we describe briefly below the three study arms and three time points of data collection. More description is provided in the Study Procedures section. (See Figure 1, page 11)

Table 1. Brief Description of Three Study Arms/Groups

Arm	Short Name	Component 1	Component 2	Component 3
		Training onsite (BAB, HBB) of providers, simulators left at facility	Peer Practice Coordinator (PPC) is trained and expected to hold weekly onsite practice sessions with providers	Mobile messages remind all trained providers to practice scenarios; and PPC has weekly mobile support from district trainer
1	Training-only	Yes	No	No
2	Partial Package	Yes	Yes	No
3	Full Package	Yes	Yes	Yes

Hypotheses

Overall Hypothesis: The partial package intervention (one-time, onsite training of providers, combined with low-dose, high-frequency peer-led practice sessions) and the full-package intervention (adding reminders and mobile support) will lead to significant gains in provider competencies (between immediately post-intervention to midline) and provider performance of key interventions *BAB* and *in HBB*, which are both maintained once the active intervention ceases.

Specific Hypotheses:

In BAB and in HBB related to the primary outcomes (see Section 4b5):

1. Provider competencies and performance will not decline (i.e. will be non-inferior) between midline and endline in the *full* package group.
2. Provider competencies and performance will not decline (i.e. will be non-inferior) between midline and endline in the *partial* package group.
3. At endline, the provider competency level and the performance level of the *partial* package group will be significantly higher than those of the training-only group.

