16	Semi-structured interview guide: Health care providers	Health care providers will be asked about their experiences with the program and their ideas for how to improve care for postpartum hemorrhage and neonatal asphyxia.
17	Semi-structured interview guide: Stakeholders	Stakeholder will be asked about their opinions about how to strengthen and sustain this program and other efforts to improve care for postpartum hemorrhage and neonatal asphyxia in Uganda.

3) *Number of study contacts* or visits required of participants.

Please see table 2 on page 5 for details. Briefly, women in labor, key stakeholders and facility in-charges will each have a maximum of only one study contact. Providers could have up to 12 study contacts, if they were selected for all types of data collection, but this will be rare. Similarly, peer practice coordinators could have up to 12 study contacts plus regular telephone contact with a member of the research team.

4) **Expected duration of the study.**

After JHSPH IRB and Ugandan IRB are obtained, the study will take 18 months.

5) A brief **data analysis plan** and description of the **nature of the variables** to be derived.

Primary Outcome:

- For the postpartum hemorrhage component, the primary outcome will be the proportion of women who received **oxytocin** (at correct dosage) within one minute of a vaginal birth, before delivery of the placenta. Data for this outcome will be obtained from the direct clinical observations.
- For the neonatal asphyxia component, the primary outcome will be the proportion of babies not breathing at birth who are breathing or being ventilated by one minute.

Secondary Outcomes:

- Change in providers' knowledge and competence related to postpartum hemorrhage and neonatal resuscitation, as assessed by knowledge tests and observed performance with a simulator.
- Trends in PPH and neonatal asphyxia/mortality rates, by abstracting *aggregated* monthly service statistics from each facility.
- Identification of structural, environmental and behavior factors that are associated with routine, frequent practice with the simulator.

Data will be entered using [name]/Foxpro/SPSS/CsPro and analyzed using Stata 12.

Quantitative data analysis

Specific Hypotheses:

In BAB and in HBB related to the primary outcomes (see Section 4b5):

1. Provider competencies and performance will not decline (i.e. will be non-inferior) between midline and endline in the *full* package group.

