2. Provider competencies and performance will not decline (i.e. will be non-inferior) between midline and endline in the *partial* package group.
3. At endline, the provider competency level and the performance level of the *partial* package group will be significantly higher than those of the training-only group.
4. At endline, the provider competency level and the performance level of the *full* package group will be significantly higher than those of the training-only group.

Hypotheses 1 and 2:

This is a non-inferiority analysis. Two-sided 90% confidence intervals (CI) for the difference in average knowledge and competence scores between midline and endline will be constructed, separately for full and partial package groups. Non-inferiority will be determined comparing the upper bound of the 90%CI for the difference between the 2 time points to the pre-specified non-inferiority margin of 0.06 (22). If the CI's upper bound is less than the predefined margin, then we are able to claim non-inferiority of the endline knowledge scores to the midline knowledge at a 0.05 level of significance.

We will first examine the differences in sample means of knowledge scores between midline and endline not adjusted for any potential confounding variables. The confidence intervals for the knowledge scores will be calculated using generalized linear models with knowledge and competencies as the dependent variables and time variable (endline vs. midline) as the primary independent variables. To account for repeated observations within providers at midline vs. endline, we will use robust Huber/White estimate of variance implemented in STATA through 'vce' (cluster) option. In addition, adjusted 90% CI for the difference in means will be constructed by adding provider- and facility-level factors in the model.

Hypotheses 3 and 4:

We will examine differences in competencies and performance at endline between the 3 study groups using generalized linear models. The dependent variables in these models will be:

- 1) knowledge and competency scores,
- 2) proportion of women who received **oxytocin** (at correct dosage) within one minute of a vaginal birth,
- 3) proportion of women whose placenta was inspected within 16 minutes, and
- 4) proportion of newborn checked for breathing within 1 minute.

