The primary independent variable will be the study group represented as 2 indicator variables for full and partial training package with training-only as the reference group. For these hypotheses, we will only use endline data. Additional variables, related to provider- and facility characteristics predictive of these outcomes, such as cadre, number of years of provider's experience, and number of prior births attended in last 90 days, will be also included in the model. Analysis of residuals will inform whether the assumptions of the generalized linear model, such as normality and homoscedasticity of residuals as well as linear fit, are satisfied.

Additional analyses will include:

1. At baseline, midline and endline we will collect data from **all study facilities** consisting of service delivery statistics, and facility inventory. These data will be analyzed using population-average marginal generalized linear models estimated using generalized estimating equations (GEE) with exchangeable working correlation structure to account for repeated observations within facilities. The dependent variable will be service delivery statistics. The independent variables will include time (represented as 2 indicator variables for midline and endline with baseline as the reference group), study group (represented as 2 indicator variables for full and partial training groups with training-only as the reference group), and interaction terms (study group by time). The interaction terms will be examined to assess whether there are differences between study groups that change significantly over time.
2. Providers who are trained will keep **logs of their practice sessions**. This is process evaluation data. These data (for example on number of times a scenario is practiced) will be compared across the three study groups using generalized linear models with Poisson or Negative Binomial distribution for the outcome.
3. **Routinely collected data from health facility registers** (recorded daily but aggregated monthly) on services provided to clients and health outcomes (discharge, or deaths and stillbirths) will be analyzed using longitudinal data analysis to account for repeated observations at each facility. This will be for population-averaged marginal generalized linear models using generalized estimating equations (GEE) and exchangeable working correlation structure.

Qualitative Analysis

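### Hypotheses 1 and 2 claim maintained performance on the primary outcomes, but the analysis written for them covers only secondary scores, and the stated power does not fit the tabled oxytocin levels

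*Combined protocol and SAP*

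**What the plan says.** The overall hypothesis in Section 1 is that gains in competencies and performance are ones "which are both maintained once the active intervention ceases". The specific hypotheses, in Section 1 and again in Section 4b5, are introduced with "In BAB and in HBB related to the primary outcomes (see Section 4b5". Hypotheses 1 and 2 then read "Provider competencies and performance will not decline (i.e. will be non-inferior) between midline and endline in the" full and partial package groups respectively.

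Section 4b5 names two primary outcomes. For postpartum hemorrhage (PPH) it is oxytocin within one minute of vaginal birth, taken from direct observation. For HBB, "the primary outcome will be the proportion of babies not breathing at birth who are breathing or being ventilated by one minute". The secondary outcomes include change in providers' "knowledge and competence related to postpartum hemorrhage and neonatal resuscitation, as assessed by knowledge tests" and simulator performance.

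The analysis for Hypotheses 1 and 2 is: "Two-sided 90% confidence intervals (CI) for the difference in average knowledge and competence scores between midline and endline will be constructed". It gives a margin of 0.06, a 0.05 level, a generalized linear model and a claim rule, all for scores.

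Oxytocin is a dependent variable only under Hypotheses 3 and 4, where the plan says "For these hypotheses, we will only use endline data". The newborn item on that list is "proportion of newborn checked for breathing within 1 minute".

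Section 3c, Table 5 note (a), justifies 378 full-arm births at midline and at endline by a within-group non-inferiority calculation on oxytocin: margin -0.1000, level 0.0250, 80% power, intra-class correlation (ICC) 0.005, 54 facilities. It puts the full-arm midline level at 70% and cites the table before it. Tables 4 and 5 show 75% at midline and 70% at endline.

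**The concern.** The hypothesis, the sample size and the analysis do not describe the same test. Followed as written, Section 4b5 would support the conclusion that performance lasts after the active intervention with written tests and simulator scores. Neither primary outcome would have a stated test of maintenance, and one of them would have no stated analysis at all. With model, variance and claim rule for oxytocin left open, they could be settled after the data are seen.

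The power statement adds a second problem. A reader who takes 80% together with Table 4 would believe the trial is likely to show non-inferiority at the levels the sponsor expects. It is not.

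**Working it through.** **1. The two non-inferiority rules side by side**

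| Element | Section 4b5, Hypotheses 1 and 2 | Section 3c, Table 5 note (a) |
|---|---|---|
| Endpoint | mean knowledge and competence scores (secondary) | oxytocin proportion (PPH primary) |
| Arms | full and partial | full only |
| Margin | 0.06 | 0.10 |
| Level | 0.05 (two-sided 90% interval) | 0.025 |
| Model and claim rule | given | not given |

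The additional analyses in Section 4b5 cover service statistics and facility inventory, practice logs, and register data. They name neither primary outcome. For the partial arm, Table 5 lists 189 births per time point and no midline-endline comparison, so Hypothesis 2 on performance has neither a sizing nor a test.

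**2. Reproducing 378**

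Inputs from note (a): 70% at both times, margin 0.10, level 0.025 taken as one-sided, 80% power, ICC 0.005, 54 facilities.

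- Independent births per time point: (1.960 + 0.842)² × 2 × 0.70 × 0.30 / 0.10² = 330.
- Design effect with m births per facility: 1 + (m - 1) × 0.005. At m = 7 it is 1.03, and 330 × 1.03 = 340.
- Whole births per facility: 54 × 6 = 324 falls short (power 78%); 54 × 7 = 378 suffices.

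So 378 is right for no change at 70%. Rounding up to whole births lifts power from 80% to 84%.

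**3. Power under the tabled levels**

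Power = Φ((d + 0.10)/SE - 1.96), where d is endline minus midline, SE = √[(p₁q₁ + p₂q₂) × DE / n], DE = 1 + (n/54 - 1) × 0.005, and the two time points are treated as independent.

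- Full arm, n = 378, DE = 1.030, 70% and 70%: SE = √(0.42 × 1.030/378) = 0.0338; power 84%.
- Full arm, 75% to 70%: SE = √(0.3975 × 1.030/378) = 0.0329; 0.05/0.0329 - 1.96 = -0.44; power 33%.
- Partial arm, n = 189, DE = 1.0125, 65% and 65%: SE = √(0.455 × 1.0125/189) = 0.0494; power 53%.
- Partial arm, 65% to 60%: SE = √(0.4675 × 1.0125/189) = 0.0500; power 17%.

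Over 27 to 54 facilities and ICC 0.005 to 0.01, the four figures stay within 81-84%, 31-33%, 51-53% and 16-17%. The facility count does not drive the result.

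In terms of data, the 95% half-width in the full arm is 1.96 × 0.0329 = 0.0645, so the rule is met only if the observed fall is at most about 3.5 points. In the partial arm the half-width is 0.097 to 0.098, which allows 0.2 to 0.3 points.

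**4. Borrowing the score rule does not help**

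With margin 0.06 and level 0.05 applied to oxytocin in the full arm, power is 55% with no change at 70% and 9% for 75% to 70%. The score rule was not what the 378 births were sized for.

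**5. Direction of the score difference**

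The rule claims non-inferiority when the upper limit is below +0.06. Read as endline minus midline, an observed gain of 0.06 or more would always fail, while every observed decline has a point estimate on the passing side. The rule therefore works only as midline minus endline, yet the model's time variable is set up as endline against midline.

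**The case against.** The strongest reply is that this is one combined document. The sample-size note fixes the oxytocin endpoint, the contrast, the margin and the level; Section 4b14 refers back to it for power; and Section 4b5 is offered only as a brief plan. This has force. A reader might infer that the oxytocin test will never be carried out, and the documents do not support that. They support only that the analysis plan does not specify it: no model, variance or claim rule is written. Since Section 4b5 does supply all of these for secondary scores, brevity does not explain the gap.

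Second, the newborn item under Hypotheses 3 and 4 is not a stray substitute. Objective 3 in Section 1 defines provider performance to include checking newborns for breathing (item c), and the HBB primary outcome sits under Objective 4 as case management (item c). That explains where the list came from. It does not remove the conflict, because the hypotheses are expressly tied to the primary outcomes and one of these is left without a model.

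Third, a mean score and a proportion may properly have different margins and levels. A reader might take 0.06 against 0.10 as an error; on its own it is not.

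Fourth, sizing non-inferiority at equal proportions is conventional, and 378 is not a miscalculation. What stands is that note (a) attributes 70% at midline to a table that says 75%, and that the tabled values imply a fall of half the margin.

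Nor should the larger full-arm sample be read as wasted: the endline births also serve Hypothesis 4.

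**Conclusion.** Wrong as written. The non-inferiority analysis for Hypotheses 1 and 2 covers only secondary scores; the oxytocin test that sized the full arm is missing from the analysis plan; and the HBB primary outcome is in no named model. Separately, the full-arm midline level in note (a) contradicts Tables 4 and 5. The 80% power holds for no change at 70% (84%) and is about 33% for the tabled 75% to 70%. In the partial arm, the same rule would have 53% with no change at 65% and 17% for the tabled 65% to 60%.

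The textual findings need no assumption. The power figures use a normal approximation, the stated ICC and facility count, and independent time points; positive correlation within facilities over time would raise them somewhat. The 54 facilities of note (a) are also assumed for the partial arm. The documents do not give the share of babies not breathing at birth, so the precision available for the HBB primary outcome cannot be derived from them. A reader might infer that its sample is demonstrably too small for a non-inferiority claim; the supported statement is only that no margin or sizing exists for it.

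**What to change.** 1. **Oxytocin.** Add to the Hypotheses 1 and 2 analysis a midline-endline model with variance clustered on facility. In the full arm, claim non-inferiority if the lower limit of the two-sided 95% interval for endline minus midline is above -0.10, which is the sponsor's own sizing rule. In the partial arm, report the same difference and interval, and either apply the same rule with its power disclosed or limit Hypothesis 2 on performance to estimation.
2. **Power.** Reconcile the midline value in note (a) with Tables 4 and 5, and state full-arm power on both assumptions.
3. **HBB primary outcome.** Add it to the outcome list for Hypotheses 3 and 4 and report its midline-endline change with a 95% interval. Make no non-inferiority claim for it unless a margin is pre-specified. Reconcile the tie to the primary outcomes with the Objective 3 and Objective 4 definitions.
4. **Scores (clarification).** State the direction of the difference. The 0.06 margin and 0.05 level can stay.

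The cost is wording in the analysis plan and a less favourable stated power. No births are added. For scale, 80% power in the full arm under 75% to 70% would need 7.849 × 0.3975/0.05² = 1,248 independent births, or about 1,404 per time point at 26 per facility (design effect 1.125); the fix does not ask for that.

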- (a) Pre- and post-training, providers will be assessed on knowledge and OSCE competency tests. There will be separate one-day trainings for BAB & HBB spaced 2 months apart.
- (b) At midline and endline providers will be given BAB and HBB knowledge tests and OSCE skills tests. Facility readiness assessments will also occur at these time points.
- (c) The number of providers in this table is taken from the ACTUAL number of providers that we are aware exist in the Eastern and Western region that attend births. All providers are invited to participate in the intervention and may be assessed.

Direct Clinical Observation: Number of births (women and newborns) to be observed

We specify the sample size of number of births to observe below. The outcome variable is: the percentage of women who **received oxytocin** in correct dose immediately after vaginal birth in three study arms. The hypothesized levels of this variable at each time point are presented below:

Table 4. Hypothesized levels of “percent of women who **received oxytocin** in correct dose “within 1 minute of vaginal birth” in three study arms

Study Arm	Baseline	Midline	Endline
Full	50% (a)	75%	70%
Partial	50%	65%	60%
Training-only	50%	55%	50%

Note:

- (a) A study carried out in 2007 (POPPHI, 2007) found that **20%** of women delivering at health facilities in Uganda received an oxytocin injection between birth and the delivery of the placenta. However, given the small sample size (n=259 births observed) and the fact that the situation may have improved (as it has in many countries), we have conservatively estimated baseline coverage of oxytocin use to be **50%**.

Table 5. Number of **births** to observe (women in labor and delivery)

Study Arm	Baseline	Midline	Endline	Total births
Full Intervention Group (expected: 50% at baseline to 75% at midline to 70% at endline)	189 67 to compare baseline-midline	378 (a) for midline-endline comparison 99, midline-only comparison 67 to compare baseline-midline	378 (a) for midline-endline comparison 189 endline-only (b)	1134
Partial Intervention Group (expected: 50% at baseline to 65% at midline to 60% at endline)	189 to compare baseline-midline	189 , to compare baseline-midline 99, midline-only comparison	189 , endline-only comparison (b)	567
Training-only Group (expected: 50% baseline to 55% at midline to 50% at endline)	189	189 , midline-only comparison	189 , endline-only comparison (b)	567
Grand Total	567	756	756	2079

Notes

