- (a) The number of **378 births** is recommended for each time point in the full package group only. N=378 is based on calculations for midline and at endline is based on a (within-group) non-inferiority calculation in the intervention group. We set the number of health facilities at 54 (9 facilities on average per district * 3 districts * each of 2 regions). This sample size will achieve 80% power to detect a non-inferiority margin difference between the group proportions of providing oxytocin of -0.1000. As shown in the previous table, the percent of deliveries with oxytocin provision at midline (post-intervention) is hypothesized to be 70% in Full group. We assume intra-class correlation (ICC) of 0.005 and significance level of the test is 0.0250.
- (b) The number of **189 births** in each group at endline (only) is based on the following assumptions: This is a two-sample comparison of proportions. We aim to detect a 15% point difference at endline between an intervention group and the training-only group. Training-only group value set at 50%, as this is most conservative. Intervention group value set at 65%. Power is set at 80%. ICC is set at 0.01.
- (c) To avoid oversampling, and to compensate for different caseloads at different facilities, the study team will be given a target number of births to observe and they will stop when they reach this target. There will be no overlap in the number of women observed, because different women will be observed at different time points.

Service Statistic Data Abstraction

There is no sample size calculation for analysis of service delivery statistics because baseline data from the study health facilities are not available.

Qualitative Data: Focus Group Discussions and In-depth Interviews

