After a 2-month period of LDHF practice and consolidation of learning, the second one-day training intervention for newborn asphyxia will take place in the facility.

Intervention: Helping Babies Breathe

The second module, “Helping Babies Breathe” (HBB), is designed to increase newborn survival by improving recognition and basic interventions for babies who do not breathe at birth. HBB focuses on routine care after healthy birth, initial steps of help to breathe at birth, ventilation with bag and mask, and ongoing care after resuscitation. Again, to ensure retention and improved performance, for two of the study arms (the same two as above) training will be followed by ongoing LDHF simulation practice conducted by the same PPCs at the facility who were trained to provide LDHF practice support after the PPH intervention (the 3rd study arm will have the newborn simulator left at the facility with a recommended schedule for practice.) As above, the intervention arm receiving the mobile phone support for PPH will receive mobile phone support for newborn resuscitation.

During the intervention period, the investigators will work with ministry of health officials to ensure adequate supply of oxytocin, and supplies related to neonatal resuscitation.

Evaluation Activities:

Data collected at baseline, midline and endline include: facility assessment, provider knowledge and skills assessment (using a simulator), and direct clinical observation. Baseline data will be collected before the one-day training in BAB. Midline data will be collected after the training and 8-weeks of practice for BAB and HBB, plus the 4 weeks of combined practice. Endline data will be collected six months after the end of the combined practice sessions.

Times of Data Collection

- Data will be collected at the facilities (facility readiness assessments and observation of provider performance) at baseline prior to any intervention that involves providers or

training. Each visit will take place over 2 or 3 days to a health facility. During this baseline visit time the provider knowledge tests and skills stations (OSCEs) for HMS:BAB and HBB will also be administered.

- On the day of training, data will be collected pre and post-training from training participants. This includes knowledge and OSCEs. BAB and HBB trainings will occur separately at different times.
- Following training and during approximately five months of the active intervention phase:

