 - Designated Peer Practice Coordinators (PPC) will log their weekly practice sessions on logs (full and partial arms only).
 - Data on the number of reminders that are sent to providers will be recorded, along with logs of calls between trainers and PPCs (full arm only).
 - Aggregated HMIS data related to PPH, newborn care and mortality data will be collected from routine and supplemental HMIS forms.
- When the five months of the active intervention phase is over, then there will be a midline assessment of providers and facilities: this will again involve a facility assessment, provider knowledge test and OSCEs, observation of provider performance, and qualitative data collection at some facilities. This will take place over 2 or 3 days.
- During the same time period, the research team will contact stakeholders by telephone to schedule interviews with them. Then the interviews will be conducted at the stakeholders' offices or another location, if requested by the stakeholder.
- Following the midline assessment, there will be a 'dormant' phase of no active intervention. This is to determine if competencies and performance is maintained by low-dose high-frequency practice in the absence of donor support. We will return six months later for an endline assessment, which is the same as the midline assessment except there will be no qualitative component.

Table 7. – Description of Data Collection Instruments

Tool #	Title	Content
1	Health Worker Listing	Name and cadre for each health worker at each facility. This will be used to generate a unique ID for each provider
2	Facility Inventory	Information about the tools and equipment available at the facility related to the study intervention, such as the availability of uterotonic drugs and neonatal resuscitators.
3	Direct clinical observation tool	Structured checklist that observers will use to take notes on the care provided to women and neonates, including routine care and treatment for postpartum hemorrhage or neonatal asphyxia.
4	Supplemental maternity register	Note: We will provide this register to facilities, but Jhpiego researchers will not abstract individual records from this document (facility staff will do this). This register collects data about each birth that is relevant to this study, such as whether a woman was diagnosed with postpartum hemorrhage and whether a newborn received bag & mask resuscitation.

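### Hypotheses 1 and 2 judge maintenance by within-arm change alone; crediting the support package for it also needs the training-only arm's change

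*Combined protocol and SAP*

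**What the plan says.** Hypotheses 1 and 2 state that competencies and performance will be non-inferior at endline to midline, in the full and the partial arm respectively. Section 4b5 gives the analysis: intervals for the difference in mean knowledge and competence scores "between midline and endline will be constructed, separately for full and partial package groups", from generalized linear models that take the "time variable (endline vs. midline) as the primary independent variables". The upper limit of a two-sided 90% interval is compared with a "pre-specified non-inferiority margin of 0.06". An adjusted version adds provider and facility factors. Neither version uses training-only data or has an arm term.

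Section 4b2 (Times of Data Collection) gives the purpose of the six-month dormant phase after midline: "This is to determine if competencies and performance is maintained by low-dose high-frequency practice in the absence of donor support".

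Training-only goes through the same two visits. Its row in Table 5 reads "Training-only Group (expected: 50% baseline to 55% at midline to 50% at endline", with 189 births at each visit, and the knowledge and simulator tests in section 3c are a census of birth attendants at each facility. In section 4b5 this arm is the reference group for Hypotheses 3 and 4, which use endline data only. The plan's one group-by-time model is an additional analysis of service delivery statistics.

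On supplies, section 4b2 says: "During the intervention period, the investigators will work with ministry of health officials to ensure adequate supply of oxytocin", and the same for resuscitation supplies. It does not limit this to one arm.

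**The concern.** The stated purpose is causal, but the test has no comparator. Whatever changes between midline and endline in all arms goes into the full-arm and partial-arm results: calendar time, repeated testing on the same instruments and staff turnover. If supply work ends with the intervention period, drug and equipment stock belongs on that list too. Adjusting for provider and facility factors does not remove a time effect shared by all facilities.

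Two wrong conclusions are possible. A favourable background trend could be reported as practice sustaining performance. An unfavourable one could be reported as the package failing to last. The data that would separate these cases are already to be collected in training-only, but no planned test of these outcomes uses that arm's change since midline.

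**Working it through.** The arithmetic uses observed oxytocin use, because that is the only outcome for which the plan gives expected levels. The argument applies equally to the scores.

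**Inputs.** From Tables 4 and 5, midline to endline: full 75% to 70% (378 births per visit), partial 65% to 60% (189), training-only 55% to 50% (189). From Table 5 note (a): margin 0.10, one-sided 0.025, ICC 0.005, 54 facilities, and "This sample size will achieve 80% power to detect a non-inferiority margin difference between the group proportions of providing oxytocin of -0.1000".

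**1. The plan's own figure.** Taking 70% at both visits, n = 2 × 0.70 × 0.30 × (1.960 + 0.842)² / 0.10² = 330. With 7 births per facility the design effect is 1 + 6 × 0.005 = 1.03, giving 340, or 6.3 per facility. Rounded up, 7 × 54 = 378. The stated number reproduces, and its inputs come from one arm with no comparator.

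**2. How the within-arm result responds to a shared shift.** Let the full arm start at 75% and let all arms move by s, so that the package has no effect on the change. The chance of concluding maintenance is Φ[(0.10 + s)/SE − 1.96], with SE = √{1.03 × [0.75 × 0.25 + p(1 − p)]/378} and p = 0.75 + s.

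| Shared shift s | Chance of meeting the 0.10 margin | Difference in change |
|---|---|---|
| +5 points | 99.8% | 0 |
| 0 | 88% | 0 |
| −5 points | 33% | 0 |
| −8 points | 9% | 0 |
| −10 points | 2.5% | 0 |

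With the section 4b5 settings instead (margin 0.06, one-sided 0.05), the chances at +5, 0, −5 and −10 are 97%, 59%, 9% and 0.2%. Under either setting the result follows the shared shift.

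**3. The contrast under the plan's expected levels.**
- Full minus training-only: (70 − 75) − (50 − 55) = 0. The gap is 75 − 55 = 20 points at midline and 70 − 50 = 20 at endline.
- Partial minus training-only: (60 − 65) − (50 − 55) = 0. The gap is 10 points at both visits.

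The plan therefore expects each advantage to be fully kept.

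**4. Precision of the contrast with the planned births.**
- Full: SE = √[(0.1875 + 0.2100)/378 + (0.2475 + 0.2500)/189] = 0.061; 95% half-width 11.9 points.
- Partial: SE = √[(0.2275 + 0.2400)/189 + (0.2475 + 0.2500)/189] = 0.071; half-width 14.0 points.
- With the 1.03 design effect applied throughout (an assumption for the other arms), the half-widths are 12.1 and 14.2. If the true contrast is zero, power to exclude a 10-point loss of advantage at one-sided 0.025 is 37% (full) and 28% (partial). For 80% power, about 724 and 781 births per arm and visit would be needed.
- Assignment is by district: 12 districts over 3 arms, so 4 per arm. Clustering at that level is not in these figures, so they are optimistic.

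**The case against.** The best defence is that Hypotheses 1 and 2 say only that levels will not decline. A within-arm estimate is a legitimate answer to whether the level held without support, and loss of support is part of the condition being studied. Hypotheses 3 and 4 then compare each package arm at endline with concurrent training-only districts, assigned by drawing lots, which share the calendar period and supply environment. That is a controlled test of whether a benefit is present six months on. All of this stands. What remains is that an endline difference does not show whether the midline advantage was kept, grew or eroded.

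Three stronger readings are tempting, and the documents do not support them.

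- *That supply support is withdrawn and a stock-out would be read as lost performance.* Section 4b2 places the supply work in the intervention period and calls the later phase one without active intervention, which implies an end but does not state it. No stock-out rate is given. Stock-outs at 5/75 = 6.7% of endline births would produce the 5-point fall, and at 10/75 = 13.3% a 10-point fall, but only if stock was complete at midline, use was nil without stock and use stayed at 75% elsewhere. Stock would also hardly affect the written and simulator scores named in the section 4b5 paragraph.
- *That equal 5-point falls mean the package does nothing for maintenance.* Step 3 shows the opposite: a zero contrast means that the 20-point and 10-point advantages are preserved.
- *That training-only is unused.* It is unused only for change in these outcomes.

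The contrast also does not isolate practice as such. Training-only facilities keep the simulators, have a recommended schedule and are encouraged to practise (sections 4b2 and 4b10), so it concerns peer and mobile support.

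**Conclusion.** The concern holds as a limit on attribution. Hypotheses 1 and 2 as analysed can show that the level held; they cannot support the section 4b2 conclusion that practice maintained it. No planned test of these outcomes uses the training-only change. This does not invalidate the within-arm result or Hypotheses 3 and 4, and it does not depend on whether supply support ends.

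On size, a shared shift between +5 and −10 points moves the full arm's chance of meeting the 10-point margin from 99.8% to 2.5% with no package effect on the change. These figures assume the expected levels in Table 4, a shift equal in percentage points across arms, and no district clustering. The contrast that would address attribution has a 95% half-width of about 12 points (full) and 14 (partial) before clustering, so it will often be inconclusive. The point is a cheap improvement to the analysis plan.

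**What to change.** In section 4b5, for the Hypothesis 1 and 2 outcomes (scores and observed performance):

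1. Report the same midline-to-endline estimate for training-only.
2. Fit midline and endline data from all three arms together, and report the arm-by-time contrast for full and for partial against training-only. Use confidence intervals that account for clustering and suit four districts per arm. The group-by-time model already planned for service statistics is the template.
3. Keep the within-arm non-inferiority result as a statement that the level held without support. Base any attribution to the package on the contrast read together with the endline comparison. Say in advance that a contrast near zero means the midline advantage was preserved, and that it concerns peer and mobile support.
4. State whether supply support continues after midline. An estimate limited to facilities with stock at the visit (Facility Inventory, Tool 2) may be added as exploratory, with the caveat that it conditions on a post-assignment variable.
5. While editing, give an explicit Hypothesis 1 and 2 analysis for observed performance, since the current paragraph describes scores only. Reconcile its 0.06 margin and 90% interval with the 0.10 margin and 0.025 level in Table 5 note (a).

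The cost is wording; the data are already to be collected. The drawback is that the contrast is imprecise, so the attribution claim will be weaker.
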